1 INTRODUCTION

1.1 Background

Successful human reproduction is dependent upon the influence of progesterone on endometrial structure and receptivity. Once the corpus luteum is formed after ovulation, it begins to secrete progesterone, which is necessary and sufficient to decidualize the endometrium to facilitate implantation. If conception and implantation occur, increasing concentrations of human chorionic gonadotropin (hCG) drive continued secretion of progesterone from the corpus luteum, which is critical for the maintenance of early pregnancy and the endometrium (Penzias, 2002). Progesterone continues to be produced by the corpus luteum until the seventh or eighth week of gestation, at which time the placenta becomes the primary site of production for the remainder of pregnancy.

Unfortunately, not all women of reproductive age are able to become pregnant or maintain a pregnancy; indeed, 12 percent of women of reproductive age in the United States have received an infertility service at some time in their lives. The administration of exogenous progesterone to support luteal function has been utilized in the treatment of infertility, particularly with assisted reproductive technology (ART). Assisted reproductive technology generally involves the surgical removal of eggs from a woman's ovaries, fertilizing them with sperm in the laboratory, and then returning them to either the donor woman's or another woman's uterus (Centers for Disease Control, 2005). For many women, in conjunction with ART, steps must be taken to prime the uterus for implantation and to sustain the pregnancy after implantation. Many tools have been developed to aid in this process.

In the middle of the 1980s, gonadotrophin-releasing hormone (GnRH) agonists were incorporated into ovarian stimulation regimens and are associated with improved outcomes after in vitro fertilization (IVF) and other ARTs. These GnRH agonists work by suppressing the pituitary and preventing premature surges of endogenous luteinizing hormone (LH) during IVF cycles and allowing time for a larger number of oocytes to reach maturity prior to harvesting. However, GnRH agonists inhibit the corpora lutea in these cycles and may create an iatrogenic luteal phase defect. Use of a GnRH agonist causes suppression of pituitary LH secretion for as long as 10 days after the last dose, and pituitary function may not return completely until 2-3 weeks after the end of therapy. Without this LH signal, the corpus luteum may be dysfunctional, and subsequent progesterone and estrogen secretion may be abnormal, compromising endometrial receptivity and potentially leading to decreased implantation and pregnancy rates (Pritt, 2002).

Various hormones, including estrogens, progesterone, and hCG have been used during the luteal phase and beyond in IVF cycles for luteal phase support. A 1994 meta-analysis showed that the use of hCG or progesterone led to significantly higher pregnancy rates than placebo (Soliman, 1994). Most treatment protocols advocate the use of progesterone throughout the first trimester of pregnancy, since corpus luteum activity has been demonstrated up to Week 10 of pregnancy, although progesterone supplementation continuing beyond a positive serum pregnancy test may not be needed. The goal of progesterone supplementation is to assist a corpus luteum that may have become compromised during ovulation induction or oocyte retrieval (Penzias, 2002).

Moreover, the vaginal route of progesterone administration has been shown to allow effective targeted delivery for various indications, including supplementation of corpus luteal function. The vaginal route offers several important advantages over other methods: it is convenient and acceptable for many patients, is not painful, does not require any special equipment, systemic levels are low, and it rarely produces allergic or other adverse reactions. Therefore, a flexible, non-degradable progesterone vaginal ring (PVR) has been developed, releasing an average of 11 mg progesterone/day consistently over 7 days. The progesterone (20% w/w) is in a micronized formulation and dispersed evenly throughout the ring.

1.2 Scientific Justification for Conducting the Trial

In a pivotal phase 3 trial (Teva Women's Health, Inc. Study DR-PGN-302) evaluating the efficacy and safety of a progesterone vaginal ring (PVR) used for luteal phase support in women undergoing IVF, the primary endpoint was clinical pregnancy rate at 8 and 12 weeks of pregnancy. Once weekly PVR was statistically non-inferior to the active comparator, daily 8% progesterone vaginal gel, in women 18-34 years of age. Secondary efficacy analyses included evaluations of live birth rate, cycle cancellation rate, rate of spontaneous abortion, rate of biochemical pregnancy, and rate of ectopic pregnancy for each treatment group. These rates were similar between the 2 active treatment groups and consistent with reported background rates. Weekly PVR insertion appeared to be safe and well tolerated. Adverse events (AEs) and serious adverse events (SAEs) were similar for both active treatment groups, and no significant safety trends were noted for PVR. Treatment-related AEs were generally similar between the 2 active treatment groups and consistent with the known safety profile of progesterone. Rates of subject discontinuation due to an AE were similar between the treatment groups. AEs related to vaginal bleeding were similar between the 2 active treatment groups. No subject discontinued because of vaginal bleeding, and no subject was switched to an alternative progesterone product because of a bleeding issue. There were no increased rates of cervical/vaginal abrasions or irritation associated with use of a vaginal ring compared with vaginal gel.

Manufacturing enhancements for the PVR were implemented subsequent to the pivotal phase 3 trial. Therefore, a bioequivalence trial was conducted to compare the PVR manufactured using the new process to the ring manufactured by the legacy process (the phase 3 clinical trial material). The results from the pharmacokinetic trial (DR201-BE-10021) demonstrated that the PVR manufactured with the new process was bioequivalent to the PVR produced from the legacy process. The safety data indicated that both rings were similarly safe and well tolerated by healthy, postmenopausal female subjects who were pretreated with estrogen.

The present trial assesses the safety and tolerability of the PVR manufactured with the new process when used for luteal phase support in women undergoing ART. While the design of the proposed trial is similar to that of the pivotal phase 3 trial for the PVR, changes to the way in which AEs are collected and scored have been implemented as requested by the Agency.

1.3 Benefit / Risk Aspects

The benefit/risk aspects are expected to be similar to what is outlined in the Investigator's Brochure for the Investigational Medicinal Product (IMP), PVR, and in the appropriate package inserts for the non-investigational medicinal products: oral contraceptives, leuprolide acetate, hCG, and MENOPUR ([menotropins for injection \[package insert\], 2016](#)). The PVR offers patients a convenient, once-weekly option for luteal phase support as an alternative to twice-daily dosing or 3-times daily dosing of the progesterone vaginal insert, once-daily dosing of the progesterone vaginal gel, or once-daily intramuscular injection of progesterone in oil that are in current clinical use in the United States.

2 TRIAL OBJECTIVES AND ENDPOINTS

In this safety trial the assessment of the trial will be on the totality of safety information collected. Hence, the purpose of categorizing the endpoints as primary and secondary is for prioritising the endpoints of interest rather than tying the trial's success to the outcome of the primary objective.

2.1 Objectives

Primary Objective

- To estimate the cumulative rate of any spontaneous abortion, including spontaneous clinically recognized pregnancy loss and blighted ovum during the trial (up to Week 12 following oocyte retrieval), in subjects treated with PVR following fresh embryo transfer.

Secondary Objectives

- To describe the cumulative rate of spontaneous abortions determined at 6 and 10 weeks post-oocyte retrieval, including spontaneous clinically recognized pregnancy loss and blighted ovum, in all subjects treated with PVR.
- To describe the cumulative rate of biochemical abortions determined at 6 and 10 weeks post-oocyte retrieval in all subjects treated with PVR.
- To describe the rate of ectopic and heterotopic pregnancy in all subjects treated with PVR following oocyte retrieval.
- To describe the safety of PVR through the collection of clinical laboratory tests and vital signs in all subjects treated with PVR.
- To assess the safety and tolerability of PVR in all subjects treated with PVR.
- To determine the positive β -hCG rate of subjects treated with PVR following oocyte retrieval.
- To determine the clinical pregnancy rate of subjects treated with PVR following oocyte retrieval.

2.2 Endpoints

Primary Endpoint

- Cumulative rate of any spontaneous abortion occurring on or before 12 weeks following oocyte retrieval in all subjects treated with PVR and undergoing fresh embryo transfer.
Note: spontaneous abortion is defined as two positive β -hCG tests occurring at least two days apart on or after 2 weeks post-oocyte retrieval, but followed by observation of any empty intrauterine gestational sac (blighted ovum), intrauterine gestation without a fetal heart beat, or absence of viable fetuses, as documented by transvaginal ultrasound (TVUS).

Secondary Endpoints

- Cumulative rate of spontaneous abortions determined at 6 and 10 weeks post-oocyte retrieval in all subjects treated with PVR.
- Cumulative rate of biochemical abortions determined at 6 and 10 weeks post-oocyte retrieval in all subjects treated with PVR. Biochemical abortion is defined as a positive β -hCG test at 2 weeks and 2 weeks + 3-4 days post-oocyte retrieval, but followed by no observed gestational sac on a later TVUS, or followed by a negative β -hCG test.
- Rate of ectopic and heterotopic pregnancies in all subjects treated with PVR following oocyte retrieval.
- Rate of abnormal findings in clinical laboratory tests and vital signs for all subjects treated with PVR.
- Frequency, intensity/grade, seriousness, and relatedness of adverse events (AEs) for all subjects treated with PVR.
- Frequency, intensity/grade of vaginal bleeding/spotting, vaginal hemorrhage, pain, vaginal infection, and vaginal irritation for all subjects treated with PVR.
- Frequency, intensity/grade, seriousness, and relatedness of AEs associated with vaginal and cervical abrasions and lesions and with vaginal adhesions for all subjects treated with PVR.
- Frequency and reason for PVR discontinuation.
- Positive β -hCG rate (positive serum β -hCG test) at 2 weeks and 2 weeks + 3-4 days post-oocyte retrieval in all subjects treated with PVR.
- Clinical pregnancy rate (TVUS showing at least 1 intrauterine gestational sac with fetal heart beat) at 6 and 10 weeks post-oocyte retrieval in all subjects treated with PVR.

3 INVESTIGATIONAL PLAN

3.1 Overall Trial Design

3.1.1 Trial Design Diagram

A trial flow overview is provided in [Table 3-1](#).

Table 3-1 Trial Flow Overview

Screening	Suppression	Stimulation	Oocyte Retrieval	Treatment Period	Post Treatment Period
Consent and Screening	Down-regulation	Visits 1 and 2	Visit 3	Visits 4-9: Day after oocyte retrieval and ongoing pregnancy (~10 weeks) PVR1 through PVR10	Visit 10: End-of-trial visit (2 weeks after last exposure to Investigational Medicinal Product)

3.1.2 Overall Design and Control Methods

This is an open-label, single-arm, safety trial of PVR for luteal phase support in women undergoing IVF with fresh oocytes. Women between the ages of 18 and 34 years with tubal, idiopathic, male factor, ovulatory dysfunction, or endometriosis-linked infertility, who agree to be considered for inclusion in the trial, will be invited to be seen at the trial site.

Once informed consent is obtained, eligible subjects will be started on an ovarian down-regulation / suppression protocol utilizing combined oral contraceptives supplied by the site for ≥ 14 days to ≤ 21 days (based upon the site standard of care), with leuprolide acetate at a dose of 0.1 mL (500 μ g)/day beginning 4 days prior to the last birth control pill and for ≥ 10 days to ≤ 20 days; ovarian suppression is to begin in the cycle immediately prior to the ovarian stimulation cycle. After suppression, an ovarian stimulation protocol will begin on the second or third day after the start of menses with a reduction in leuprolide acetate dose to 0.05 mL (250 μ g/day) followed by an individually determined ovarian stimulation protocol with highly purified, human menopausal gonadotropin (HP-hMG; MENOPUR) at an initial dose of 225 IU/day for 5 days according to label. Based on clinical monitoring, subsequent dosing should be adjusted according to individual subject response. Dose adjustments should not be made more frequently than once every two days and should not exceed 150 IU per adjustment. The maximum daily dose of MENOPUR should not exceed 450 IU and the minimum daily dose should not be lower than 75 IU. MENOPUR dosing should not continue for >20 days and coasting is not allowed. Subjects will be monitored to determine when to trigger ovulation with hCG. A TVUS will be performed to assess follicle size and serum estradiol levels will be determined. A subject must have at least 2 follicles ≥ 17 mm (mean of 2 dimensions) to receive the hCG trigger. Subjects who do not reach this threshold after 20 days of stimulation are to be discontinued from the trial. If the estradiol level is ≥ 5000 pg/mL, hCG should not be administered and the subject should be discontinued from the trial.

Oocyte retrieval will occur approximately 35-37 hours after hCG administration. On the day after oocyte retrieval, the subject will begin treatment with the IMP, PVR. Following instruction on PVR insertion and removal (see [Appendix 1](#)), the subject will insert the first PVR (PVR1) at the trial site. The PVR will remain in place a minimum of 23 hours/day. The subject will remove PVR1 before embryo transfer and reinsert it after the transfer. Fresh embryo transfer will occur 5 days after oocyte retrieval per the trial site's protocol. The number of embryos to transfer must be guided by the 2017 American Society for Reproductive Medicine (ASRM) and the Society for Assisted Reproductive Technology (SART) guidelines (SART/ASRM 2017): women with the expectation of one or more high-quality embryo(s) available for cryopreservation, and women with previous live birth after an IVF cycle, will have transfer of a single blastocyst. All other women will have transfer of no more than two blastocysts. Additional PVRs will be distributed for weekly insertion, with the second PVR (PVR2) to be inserted at home 7 days following the initial insertion of the first PVR (PVR1), and the third PVR (PVR3) to be inserted either at home or at the site 7 days following the insertion of PVR2.

Two weeks after oocyte retrieval, a blood draw will be performed to measure serum levels of progesterone and β -hCG. Subjects with a β -hCG level <5 mIU/mL will be discontinued from the trial. Those with a β -hCG level ≥ 5 mIU/mL will insert their next PVR and continue in the trial for up to a total of 10 weeks (up to a total of 10 PVRs). Additional serum pregnancy tests will be performed at 2 weeks + 3-4 days and at 3 weeks. Subjects who are no longer pregnant will be discontinued from the trial. Subjects with positive β -hCG results at 3 weeks will insert PVR4 and receive PVR5 and PVR6 to be inserted weekly.

A TVUS will be performed to document the presence of an intrauterine gestational sac 4 weeks + 3-4 days after oocyte retrieval. If it is determined that the subject has an ectopic pregnancy, the subject will be treated according to the site's standard protocol and will be withdrawn from the trial. Six weeks after oocyte retrieval, a TVUS will be performed to determine the presence and number of gestational sacs with/without fetal heart beat. Pregnant subjects will insert PVR7 and receive additional PVRs to be inserted weekly (PVR8, PVR9, and PVR10). Ten weeks after oocyte retrieval (if the subject is pregnant), an ultrasound (either transvaginal or abdominal) will be performed to determine the number of gestational sacs present with and without fetal heart beat and the estimated gestational age.

Safety will be monitored throughout the trial. Standardized criteria will be applied to AEs of special interest (vaginal bleeding, vaginal pain, and vaginal irritation etc., see section [8.3](#)) to establish grade (intensity). Patient-reported vaginal pain and/or irritation ([Appendix 3](#)) should be recorded as an AE if considered clinically significant by the physician. The physician can perform an unscheduled pelvic examination at his or her discretion based upon these AEs at any time (see [Appendix 2](#)). A scheduled pelvic examination will be performed at screening, on day 1 of PVR treatment, and 4 weeks + 3-4 days, 6, 10, and 12 weeks post-oocyte retrieval (Visits 4, 7P, 8, 9 and 10) to document the presence and grade (intensity) of any pain, irritation, abrasions, or lesions on the cervix or vagina and the presence and grade (intensity) of vaginal adhesions using standardized criteria ([Appendix 2](#)). If any lesions or abrasions are found on the cervix or vagina or vaginal adhesions are

noted, another examination will be performed 2-4 days later. Subjects will be followed until the lesions/abrasions resolve or until the final assessment at the End-of-trial visit, whichever comes first. Any clinically significant finding will be reported as an AE.

Post-trial procedures will be performed 2 weeks after the last exposure to investigational medicinal product (IMP) (12 weeks after oocyte retrieval).

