8 ADVERSE EVENTS

8.1 Adverse Event Definition

An adverse event (AE) is any untoward medical occurrence in a subject participating in a clinical trial. It includes:

- Any unfavourable and unintended sign, symptom or disease temporally associated with the use of the IMP, whether or not considered to be caused by the IMP.
- AEs commonly observed and AEs anticipated based on the pharmacological effect of the IMP.
- Any laboratory abnormality, vital sign, or finding from physical or gynecological examination assessed as clinically significant by the Investigator (*Note*: pre-existing conditions diagnosed through assessments and examinations at the screening visit or during the screening period are not AEs, but are recorded as medical history).
- Accidental injuries, reasons for any change in medication (drug and/or dose), reasons for any medical, nursing or pharmacy consultation, or reasons for admission to hospital or surgical procedures.
- Overdoses and medication errors with and without clinical consequences.

All AEs will be coded by Ferring Global Pharmacovigilance using the Medical Dictionary for Regulatory Activities (MedDRA) (the version effective at trial start).

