8.2 Collection and Recording of Adverse Events

8.2.1 Collection of Adverse Events

The Investigator must monitor the condition of the subject throughout the trial from the time of obtaining informed consent until the last visit (End-of-trial).

The sources of AEs cover:

- The subject's response to questions about her health (a standard non-leading question such as "How have you been feeling since your last visit?" is asked at each visit).
- Symptoms spontaneously reported by the subject.
- Investigations and examinations where the findings are assessed by the Investigator to be clinically significant changes or abnormalities.
- Other information relating to the subject's health becoming known to the Investigator (e.g., hospitalization).

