8.2.2 Recording of Adverse Events

The Investigator must record all AEs in the AE Log provided in each subject's eCRF with information about:

- AE description
- Date and time of onset (time can be omitted, if not applicable)
- Intensity
- Causal relationship to IMP
- Action taken to IMP
- Other action taken
- Date and time of outcome (time can be omitted, if not applicable)
- Outcome
- Seriousness.

Each of the items in the AE Log is described in detail in the following sections.

Adverse Event

AEs should be recorded as diagnoses, if available. If not, separate signs and symptoms should be recorded. One diagnosis/symptom should be entered per record.

If a subject suffers from the same AE more than once and the subject recovers in between the events, the AEs should be recorded separately. If an AE changes in intensity, a worst-case approach should be used when recording the event, i.e., the highest intensity and the longest duration of the event.¹

Note the following: a procedure is not an AE; the reason for conducting the procedure is. Hospitalization is not an AE; the reason for hospitalization is. Death is not an AE, but the cause of death is (an exception is sudden death of unknown cause, which is an AE).

¹ Exception: if an AE with onset before the first IMP administration (i.e., a pretreatment AE) worsens in intensity, this must be recorded as 2 separate events. The initial AE should be recorded with outcome "not recovered" and the date and time of outcome are when the intensity changed. The second AE should be recorded with date and time of onset when the intensity changed.

Date and Time of Onset

The date of onset is the date when the first sign(s) or symptom(s) were first noted. If the AE is an abnormal clinically significant laboratory test or outcome of an examination, the onset date is the date the sample was taken or the examination was performed.

Intensity

The intensity of an AE must be classified using the following 3-point scale:

Mild: Awareness of signs or symptoms, but no disruption of usual activity.

Moderate: Event sufficient to affect usual activity (disturbing).

Severe: Inability to work or perform usual activities (unacceptable).

The grading of AEs of special interest will be based on predefined criteria as discussed in section [8.3](#).

Causal Relationship to IMP

The possibility of whether the IMP caused the AE must be classified as one of the following:

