Appendix 3 Assessment of AEs of Special Interest: Vaginal Pain and Vaginal Irritation

[figure not shown]
INDIVIDUAL SIGNS/SYMPOTOMS				
PARAMETER	GRADE 1 MILD	GRADE 2 MODERATE	GRADE 3 SEVERE	GRADE 4 POTENTIALLY LIFE- THREATENING
VAGINAL PAIN				
Pain	Pain causing no or minimal inference with usual social & functional activities	Pain causing greater than minimal inference with usual social & functional activities or the need for non-narcotic medication	Pain causing inability to perform usual social & functional activities or the need for narcotic medication	Disabling pain causing inability to perform basic self-care functions OR hospitalization (other than emergency room visit) indicated
Dyspareunia (pain with sexual activity)	Pain causing no or minimal inference with sexual function	Pain causing greater than minimal inference with sexual function	NA	NA
VAGINAL IRRITATION				
Vaginal itching	Itching causing no, mild or moderate inference with usual social & functional activities	Itching causing inability to perform usual social & functional activities; may require intervention such as antihistamine or bathing to provide relief	NA	NA
Vaginal dryness	Dryness causing no or minimal inference with usual sexual, social & functional activities	Dryness causing greater than minimal inference with usual sexual, social & functional activities	NA	NA
Vaginal discharge by participant report	Mild-moderate increase in amount above participant baseline – no sanitary protection required	Profuse increase in discharge requiring pad use or other hygienic intervention	NA	NA

Adapted from: Division of AIDS Table for Grading the Severity of Adult and Pediatric Adverse Events, Addendum 1 (Female Genital Grading Table for Use In Microbicide Studies); November 2007.

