A TVUS will be performed to document the presence of an intrauterine gestational sac 4 weeks + 3-4 days after oocyte retrieval. If it is determined that the subject has an ectopic pregnancy, the subject will be treated according to the site's standard protocol and will be withdrawn from the trial. Six weeks after oocyte retrieval, a TVUS will be performed to determine the presence and number of gestational sacs with/without fetal heartbeat. Pregnant subjects will insert PVR7 and receive additional PVRs to be inserted weekly (PVR8, PVR9, and PVR10). Ten weeks after oocyte retrieval (if the subject is pregnant), an ultrasound (either transvaginal or abdominal) will be performed to determine the number of gestational sacs present with and without fetal heartbeat and the estimated gestational age.

Safety will be monitored throughout the trial. Standardized criteria will be applied to AEs of special interest ([Protocol Section 8.3](#)) to establish grade (intensity). Patient-reported vaginal pain and/or irritation should be recorded as an AE if considered clinically significant by the physician. The physician can perform an unscheduled pelvic examination at his or her discretion based upon these AEs at any time. A scheduled pelvic examination will be performed at screening, on day 1 of PVR treatment, and 4 weeks + 3-4 days, 6, 10, and 12 weeks post-oocyte retrieval (Visits 4, 7P, 8, 9 and 10) to document the presence and grade (intensity) of any pain, irritation, abrasions, or lesions on the cervix or vagina and the presence and grade (intensity) of vaginal adhesions using standardized criteria. If any lesions or abrasions are found on the cervix or vagina or vaginal adhesions are noted, another examination will be performed 2-4 days later. Subjects will be followed until the lesions/abrasions resolve or until the final assessment at the End-of-trial visit, whichever comes first. Any clinically significant finding will be reported as an AE.

Post-trial procedures will be performed 2 weeks after the last exposure to investigational medicinal product (IMP) (12 weeks after oocyte retrieval).

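### A physician clinical-significance test on patient-reported vaginal pain and irritation conflicts with the protocol's own AE rules and can lower the recorded frequency of a secondary safety endpoint

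*Protocol*

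**What the plan says.** - Protocol 3.1.2, in a sentence that points to Appendix 3, says that vaginal pain or irritation reported by the subject "should be recorded as an AE if considered clinically significant by the physician". The synopsis has the same text. SAP 3.1 repeats it: "Patient-reported vaginal pain and/or irritation should be recorded as an AE if considered clinically significant by the physician".
- Protocol 8.1 includes among AEs "Any unfavourable and unintended sign, symptom or disease temporally associated with the use of the IMP", with no significance test. The test appears in a separate item, for a laboratory abnormality, a vital sign or a "finding from physical or gynecological examination assessed as clinically significant by the Investigator".
- Protocol 8.2.1 makes the same split. It lists "Symptoms spontaneously reported by the subject" as a source of AEs without a test, and attaches the test to investigations and examinations.
- Protocol 8.2.2 states: "The Investigator must record all AEs in the AE Log". Its general scale defines Mild as being aware of a symptom that does not disrupt activity.
- Protocol Appendix 3 gives Grade 1 to "Pain causing no or minimal inference with usual social & functional activities" (printed so; interference is evidently meant). Dyspareunia and dryness have a parallel Grade 1.
- Protocol 8.3.1 sends these AEs to Appendix 3 for grading. It neither repeats the significance test nor removes it.
- The note under Protocol Appendix 2 makes a pelvic-examination finding an AE when it is judged clinically significant.

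**The concern.** The two rules give different answers for the same complaint. Suppose a woman reports mild vaginal itching at Visit 6 and the physician thinks it unimportant. Under 8.1 and 8.2.2 it is a mild AE. Under 3.1.2, read in the natural way, it is not recorded. Two sites could treat the complaint differently and both be following the protocol.

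At stake is one of the secondary endpoints in Protocol 2.2, the frequency and grade of a list of local events that includes vaginal pain and irritation. The table of AEs of special interest (Protocol 9.9.2.1, SAP 10.2.3) is built from recorded treatment-emergent AEs found by preferred term, so an unrecorded complaint cannot enter it. The trial is open-label with a single arm. The absolute frequency is itself the result, and no comparator arm shares the same under-recording.

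**Working it through.** No stated figure depends on this rule, so there is none to reproduce. The check is a comparison of texts.

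**1. Do the rules conflict?**

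| Place | Patient-reported symptom | Significance test? |
|---|---|---|
| Protocol synopsis, 3.1.2; SAP 3.1 | Vaginal pain or irritation | Yes |
| Protocol 8.1 | Any unfavourable symptom | No; only laboratory, vital-sign and examination findings |
| Protocol 8.2.1 | Spontaneously reported symptoms | No |
| Protocol 8.2.2 | All AEs; Mild is awareness only | No |
| Protocol 8.3.1, Appendix 3 | Vaginal pain or irritation | Silent; Grade 1 exists |
| Protocol Appendix 2 note | Findings, including rows that are patient reports | Yes |

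They conflict, and no section says which prevails.

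**2. Which way does it act?** Recorded frequency = true frequency × share of symptomatic women whose complaint passes the test. The share cannot exceed 1, so applying the test can only lower the AE frequency. Complaints with no or minimal interference are the likeliest to be judged unimportant, so the loss probably falls mostly on Grade 1. The documents do not show this.

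**3. How large is it?** The documents give neither the true frequency nor the share that passes. The figures below are assumptions, on a round 240 subjects (the planned mITT size; the safety cohort is everyone given the ring). They show scale only.

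| Assumed true frequency | 75% pass | 50% pass | 25% pass |
|---|---|---|---|
| 10% (24 subjects) | 18 (7.5%) | 12 (5%) | 6 (2.5%) |
| 20% (48 subjects) | 36 (15%) | 24 (10%) | 12 (5%) |

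**4. Is there another record?** Pelvic-examination grades under Appendix 2 are summarized by visit whether or not an AE is recorded (Protocol 9.9.7, SAP 10.4.3). After screening, examinations are scheduled at Visits 4, 7P, 8, 9 and 10.

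- Visit 4 is day 1 after retrieval. Visit 7P is 4 weeks + 3–4 days, which is day 31–32. The nominal gap is 31 − 1 = 30 to 32 − 1 = 31 days, with Visits 5, 6, 6P and 7 inside it.
- Visit 8 is day 42 and Visit 9 is day 70, a further gap of 28 days.
- An unscheduled examination is at the physician's discretion, and 3.1.2 and 7.2.8 tie it to a reported AE.
- Neither 7.2.8 nor Appendix 2 sets a recall period, so a symptom that has resolved by the examination may not be graded.

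**5. Is there a subject log?** Bleeding has a similar significance rule (7.2.4, 8.3.5), but the Bleeding Log captures every incidence. Pain and irritation have no such log. The PVR diary (7.3.6) covers only ring dates, wear time and damage.

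**The case against.** The strongest reply is that the significance wording sits in design-overview text and says if, not only if. The operative AE sections (8.1 to 8.2.2) carry no such filter for symptoms. Section 8.3.1 states none for pain and irritation, whereas 8.3.5 does state one for bleeding. A careful site could therefore record everything. This stands as far as it goes: the protocol does not establish that mild vaginal complaints are excluded. But a test that excluded nothing would serve no purpose, and the sentence appears in three places.

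Second, other capture is better than the AE tables suggest. All five Appendix 3 symptoms also have rows in Appendix 2, and the secondary endpoint for pain and irritation is not worded as AEs, so the examination grades bear on it directly. A reader might infer that symptoms at Visits 5 to 7 reach the data only through the AE log. That is wrong. Women who stop early have graded examinations at the Early-withdrawal and End-of-trial visits (3.5.6, 6.3.8, 6.4), and unscheduled graded examinations are allowed. What remains is mainly transient symptoms in women who continue.

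Third, a reader might infer that the wording defeats the change in AE collection that the Agency asked for (Protocol 1.2). The documents do not say what was asked, so this cannot be claimed.

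**Conclusion.** The inconsistency is real and should be resolved. Where the significance test is applied, it can only reduce the AE frequency of vaginal pain and irritation, probably mostly at Grade 1, and recording may differ between sites. That conclusion needs only the text and the assumption that some sites follow 3.1.2 as a filter.

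Two stronger readings should not be drawn. One is that these events are under-counted: the documents show a route to under-counting, not that it happens or by how much, and the table of assumed figures is no evidence. The other is that these are the events the trial exists to measure. The primary endpoint is spontaneous abortion, and vaginal pain and irritation belong to one of several secondary endpoints, although Protocol 2 says the trial will be judged on the totality of its safety information. The primary analysis, power and sample size do not use this rule.

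**What to change.** In the synopsis, Protocol 3.1.2 and SAP 3.1, state that every patient-reported Appendix 3 symptom that starts or worsens after first PVR insertion is recorded as an AE and graded by Appendix 3. Keep clinical significance as a flag on the record, so that the tables can be shown with and without the complaints judged unimportant.

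Align the Appendix 2 note as well. Its significance test should apply only to what the clinician observes, and not to the patient-reported rows: pain, dyspareunia, itching, dryness, and discharge by participant report. Otherwise the same complaint would fall under opposite rules depending on whether it was voiced at a pelvic examination. The test can stay for laboratory, vital-sign and clinician-observed examination findings, as in 8.1.

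The cost is protocol and SAP wording, more Grade 1 AE records and a less favourable reported frequency. Timing limits what new wording can recover: Protocol 3.1.3 estimates the last visit in Q3 2019, and the protocol version that the SAP cites is dated 9 August 2019. If collection is nearly complete, source records can be queried for complaints not entered as AEs, and the report should state the limitation.
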